4.3 EARLY TERMINATION/SAFETY FOLLOW-UP VISIT

An early termination visit is required for any subjects who permanently discontinue study drug early for any reason including disease progression. Each subject should be followed for 30 (±7) days after his or her last dose of study drug (ie, the "safety follow-up visit") to monitor for resolution or progression of AEs (see Section 6.2.5) and to document the occurrence of any new events; unless, the subject receives a new anticancer therapy within this timeframe. Subjects who withdraw consent should still be encouraged to complete the safety follow-up assessments, but these assessments cannot be mandated once consent is withdrawn. The Schedule of Assessments (Appendix 5) describes the procedures required for the safety follow-up.

4.4 MISSED EVALUATIONS

Missed evaluations should be rescheduled and performed as close to the original scheduled date as possible. An exception is made when rescheduling becomes, in the investigator's opinion, medically unnecessary or unsafe because it is too close in time to the next scheduled evaluation. In that case, the missed evaluation should be abandoned.

5.0 STATISTICAL METHODS OF ANALYSIS

5.1 GENERAL CONSIDERATIONS

Descriptive statistics (including means, standard deviations, and medians for continuous variables and proportions for discrete variables) will be used to summarize data as appropriate. Analyses will be done by dosing regimen and overall.

5.2 SAMPLE SIZE CONSIDERATIONS

This study will assess safety, PK, PD, and antitumor activity of ACP-196 alone or in combination with dexamethasone. Subjects will be equally randomized into 1 of the 2 dosing regimens (ACP-196 monotherapy or ACP-196 + dexamethasone) as an efficient method for allocating patients into these regimens. The study is not formally designed to compare these regimens but rather to obtain descriptive information that can be used in support of further ACP-196 development.

While the primary objective of this study is to determine the safety in each of the 2 dosing cohorts, the sample size has been determine to independently evaluate the activity of each dosing regimen. The trial seeks to exclude an uninteresting ORR of $\leq 15\%$ (ie, the response rate that might be associated with single-agent dexamethasone therapy [Anderson 2013]) in favor a target response rate of $\geq 40\%$. Considering a sample size of 19 subjects per cohort, the power to detect the difference between a null-hypothesis response rate of 15% and an alternative-hypothesis response rate of 40% with a 0.025 one-sided significance level is 69% using a one-group, exact binomial test. A sample size of 19 subjects per cohort will also provide a 97.5% 1-sided confidence interval centered around an expected ORR of 40% that excludes an ORR of 18.6% as a lower bound.

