	Disease control rate				
	Progression-free survival				
Pharmacokinetic Parameters:	The plasma PK of ACP-196 will be characterized using noncompartmental analysis. The following PK parameters will be calculated, whenever possible, from plasma concentrations of analytes:				
	 AUC_{0-t}: Area under the plasma concentration-time curve calculated using linear trapezoidal summation from time 0 to time t, where t is the time of the last measurable concentration (C_t). 				
	• AUC ₀₋₁₂ : Area under the plasma concentration-time curve from 0 to 12 hours, calculated using linear trapezoidal summation.				
	• AUC _{0-∞} : Area under the plasma concentration-time curve from 0 to infinity, calculated using the formula: AUC _{0-∞} = AUC _{0-t} + C_t / λ_z , where λ_z is the apparent terminal elimination rate constant.				
	• AUC _{0-24calc} : Area under the plasma concentration-time curve from 0 to 24 hours, calculated by doubling the value for AUC ₀₋₁₂ .				
	C _{max} : Maximum observed plasma concentration				
	• T _{max} : Time of the maximum plasma concentration (obtained without interpolation)				
	 t_{1/2}: Terminal elimination half-life (whenever possible) 				
	 λ_z: Terminal elimination rate constant (whenever possible) CL/F: Oral clearance 				
Pharmacodynamic Parameters:	The occupancy of Btk by ACP-196 will be measured in peripheral blood mononuclear cells (PBMCs) and in bone marrow, when available, with the aid of a biotin-tagged ACP-196 analogue probe. The effect of ACP-196 on biologic markers of B-cell function will also be evaluated.				
Sample Size:	Forty subjects with 20 subjects in each cohort.				
Inclusion Criteria:	 Men and women ≥ 18 years of age. 				
	• A confirmed diagnosis of MM, which has relapsed after, or been refractory to ≥ 1 prior therapy for MM, and is progressing at the time of study entry.				
	• Evaluable myeloma at screening, defined as the presence of at least one of the following:				
	 Serum M-protein ≥ 0.5 g/dL 				
	◦ Urine M-protein ≥ 200 mg/24 hours				

		 In subjects without detectable serum or urine M-protein, serum free light chain (SFLC) > 100 mg/L (involved light chain) and an abnormal serum kappa/lambda ratio
		 For subjects whose disease can only be reliably measured by serum quantitative immunoglobulin A (IgA), IgA ≥ 750 mg/dL (0.75 g/dL)
	•	Eastern Cooperative Oncology Group (ECOG) performance status of ≤ 2 .

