	 Cohort 2 (BID + dexamethasone): 100 mg ACP-196 (1 x 100-mg capsule) administered 12 hours apart (BID dosing = 200-mg total daily dose) plus 40 mg dexamethasone administered once weekly (weekly dosing = 40-mg total weekly dose)
Concomitant Medications:	The effect of agents that reduce gastric acidity (eg, proton pump inhibitors, H2-receptor antagonists, or antacids) on ACP-196 absorption is currently being evaluated in a healthy volunteer study (ACE-HV-004). Preliminary results from this study suggest subjects should avoid the use of calcium carbonate containing drugs or supplements (eg, antacids or calcium supplements) and short-acting H2-receptor antagonists for a period of at least 2 hours before and after taking ACP-196. Use of omeprazole or esomeprazole or any other long-acting proton pump inhibitors while taking ACP-196 is not permitted due to a potential decrease in study drug exposure; however, if a subject requires treatment with a long-acting proton pump inhibitor while on study (eg, to treat an ulcer), treatment options should be discussed with the Medical Monitor. Concomitant use of strong inhibitors/inducers of CYP3A should be avoided when possible. If a subject requires a strong CYP3A inhibitor while on study, monitor the subject closely for potential toxicities.
Statistics:	Subjects meeting the stated eligibility requirements will be enrolled onto the study. Subjects will be randomized in a 1:1 ratio into the 2 regimens (ACP-196 with and without dexamethasone). With a sample size of 19 subjects per cohort, the power to detect the difference between a null-hypothesis response rate of 15% and an alternative response rate of 40% with a 0.025 one-sided significance level is 0.69 using a one-group, exact binomial test. A sample size of 19 subjects per cohort will also provide a 97.5% one-sided confidence interval centered around an expected ORR of 40% that excludes an ORR of 18.6% as a lower bound. Descriptive statistics (including means, standard deviations, and medians for continuous variables and proportions for discrete variables) will be used to summarize data, as appropriate.

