5.3 DEFINITION OF ANALYSIS POPULATIONS

The following definitions will be used for the analysis populations:

- Safety population: All enrolled subjects who receive ≥ 1 dose of study drug.
- Intent-to-treat (ITT) population: All subjects who have been randomized.

The safety population will be used for evaluating the safety parameters in this study. The ITT population will be analyzed for efficacy parameters in this study.

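### Power and precision are given for 19 per cohort although 20 are planned, and the 18.6% lower bound corresponds to no possible responder count (minor)

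*Protocol*

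**What the plan says.** The synopsis sets the size of the trial: "Forty subjects with 20 subjects in each cohort". Section 3.1 of both the protocol and the SAP plans forty subjects randomised 1:1. Protocol 5.3 defines the ITT population as everyone randomised and adds: "The ITT population will be analyzed for efficacy parameters in this study".

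Protocol 5.2 bases its calculation on a different number: "Considering a sample size of 19 subjects per cohort". It sets a "null-hypothesis response rate of 15" per cent against an "alternative-hypothesis response rate of 40" per cent and reports that power "with a 0.025 one-sided significance level is 69% using a one-group, exact binomial test". The precision statement follows: "A sample size of 19 subjects per cohort will also provide a 97.5% 1-sided confidence interval centered around an expected ORR of 40" per cent, excluding an ORR of 18.6% as a lower bound. The synopsis (Statistics) repeats the basis, "With a sample size of 19 subjects per cohort, the power to detect the difference", and SAP 3.2 carries the same figures.

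Neither document says why 19 is used or states a dropout or non-evaluability allowance. Protocol 3.4.3 only lets the investigators and sponsor replace, at their discretion, a subject who does not complete Cycle 2.

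**The concern.** Section 5.2 says that the cohort size was chosen so that each regimen's activity could be evaluated on its own, with the aim of excluding an ORR of 15% or less. The power and the lower bound are the only quantitative support for that choice. They are worked out for a cohort size that is neither the number planned nor the number in the protocol's efficacy denominator.

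The lower bound has a second problem that does not depend on 19 versus 20. Forty per cent of 19 is 7.6, so a figure evaluated there describes no result the trial could produce. A reader who takes 18.6% as the limit to expect will not find it in any table.

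**Working it through.** **Inputs.** Null rate 0.15, alternative rate 0.40, one-sided alpha 0.025, one-group exact binomial test, n=19 (protocol 5.2). Planned n=20 per cohort (synopsis; protocol 3.1). Exact method for binomial intervals (SAP 10.1).

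**Rule.** Reject at the smallest r with P(X ≥ r | n, 0.15) ≤ 0.025. Power is P(X ≥ r | n, 0.40).

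**The plan's own figure, n=19.**
- r=6: P(X ≥ 6 | 19, 0.15) = 0.0537, too large.
- r=7: P(X ≥ 7 | 19, 0.15) = 0.0163, so the cut-off is 7.
- Power: P(X ≥ 7 | 19, 0.40) = 0.692. This reproduces the stated 69%.

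**The planned cohort, n=20.**
- r=6: P(X ≥ 6 | 20, 0.15) = 0.0673, too large.
- r=7: P(X ≥ 7 | 20, 0.15) = 0.0219, so the cut-off is again 7.
- Power: P(X ≥ 7 | 20, 0.40) = 0.750.

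**Lower bound.** The Clopper-Pearson 97.5% one-sided lower limit is the 0.025 quantile of Beta(x, n − x + 1).

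| Responders | Observed ORR | Lower limit |
|---|---|---|
| 7/19 | 36.8% | 16.3% |
| 7.6/19 (impossible) | 40.0% | 18.64% |
| 8/19 | 42.1% | 20.3% |
| 6/20 | 30.0% | 11.9% |
| 7/20 | 35.0% | 15.4% |
| 8/20 | 40.0% | 19.1% |

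The stated 18.6% matches only the impossible row. Other methods at 40% and n=19 do not give it: Wald 18.0%, Wald with continuity correction 15.3%, Wald with a t quantile 16.4%, Wilson 21.5%, Jeffreys 20.7%, Agresti-Coull 21.6%. It is not an n=20 figure either (Wald 18.5%, exact 19.1%).

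**Centring.** A one-sided interval runs from its lower limit to 100% and has no centre at the estimate. The matching two-sided exact interval at 7.6/19 runs from 18.6% to 64.6%, with midpoint (18.6 + 64.6)/2 = 41.6%, so it is not centred on 40% either.

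**How firm 75% is.**
- If one of 20 randomised is non-evaluable, counts as a non-responder, and the other 19 respond at 40%, the 7/20 rule has power P(X ≥ 7 | 19, 0.40) = 69.2%.
- If a replacement brings the ITT denominator to 21, P(X ≥ 7 | 21, 0.15) = 0.0287 exceeds 0.025. The cut-off becomes 8 (type I error 0.0083) and power is P(X ≥ 8 | 21, 0.40) = 65.0%.

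**The case against.** The strongest reply is that nothing is miscalculated. Section 5.2 announces n=19, and 69% is right for that n. This stands: a reader might infer an arithmetic error in the power, and there is none.

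A second reply is that 19 may be an evaluable number. Protocol 4.2 defines evaluability for response, and one non-responder by default among 20 returns exactly 69.2%. The original protocol, included in the same file, also used a per-protocol efficacy set that required a post-treatment assessment. This is plausible, but no passage says it, and the current protocol's denominator is everyone randomised. It justifies offering a second form of the fix, not leaving the text as it is.

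A reader might also infer that the number of responses needed to exclude 15% cannot be worked out. It can. The null rate, alpha, sidedness, test and n fix it at 7, and it is 7 at both 19 and 20.

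On the bound, one can say that precision at an expected 40% is a planning value, not a forecast of a count, and that 19.1% differs from 18.6% by only 0.5 percentage points. The size of the difference is conceded. However, the plan calls for an exact interval, which exists only at whole counts, and 8/20 is exactly 40%, so an attainable figure was available.

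Finally, SAP 5 states that no formal hypothesis will be tested, safety is the primary objective, and SAP 3.1 records that enrolment was discontinued under a memo of March 2016. All of this limits the weight of the point.

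**Conclusion.** The point holds as a minor inconsistency. The stated power and bound belong to n=19, the planned cohort is 20, and the documents give no reason for the difference. Under the planned design the power is 75.0% against a stated 69%, with type I error 0.022 and an unchanged cut-off of 7.

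It would go too far to call 75% the trial's power without qualification. It requires exactly 20 analysed per cohort and a true ORR of 40% among all of them. SAP 6.1 and 10.7.2 use the All-treated population, so it also requires that all 20 are dosed, and replacement could change the denominator. Nor is any result put at risk: the reported analysis is an ORR with a 95% interval, and the stated power errs on the low side relative to n=20.

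The 18.6% bound is unattainable whichever cohort size was meant, and describing a one-sided exact limit as centred on 40% is incorrect.

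**What to change.** In protocol 5.2 and the synopsis, restate for the planned cohort: an ORR of 15% is excluded with 7 or more responses out of 20; exact one-sided type I error 0.022; power 75% at a true ORR of 40% if 20 are analysed. Replace the 18.6% sentence with: 8/20 responders (40%) gives a 97.5% one-sided exact lower bound of 19.1%. Drop the description of the interval as centred.

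If 19 was meant as the evaluable number, say so and why. Keep 69%, and replace 18.6% with attainable bounds: 16.3% at 7/19 and 20.3% at 8/19.

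In SAP 3.2, label the figures as the original plan, since enrolment was discontinued and the SAP analyses the All-treated population.

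The cost is wording only. No subjects, assessments or analyses are added.

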5.3 DEFINITION OF ANALYSIS POPULATIONS

The following definitions will be used for the analysis populations:

- Safety population: All enrolled subjects who receive ≥ 1 dose of study drug.
- Intent-to-treat (ITT) population: All subjects who have been randomized.

The safety population will be used for evaluating the safety parameters in this study. The ITT population will be analyzed for efficacy parameters in this study.

5.4 MISSING DATA HANDLING

General Considerations: Subjects lost to follow-up (or who dropped out) will be included in statistical analyses up to the point of their last evaluation.

Duration of Response and Progression-free Survival: Data for subjects without disease progression or death will be censored at the date of the last tumor assessment and before the initiation of alternative anticancer therapy.

Safety: Missing or partial start and end dates for AEs and concomitant medications will be imputed according to prespecified, conservative imputation rules. No other imputation of values for missing data will be performed.

5.5 ENDPOINT DATA ANALYSIS

5.5.1 Safety Endpoint

Safety summaries will include summaries in the form of tables and listings. The frequency (number and percentage) of treatment emergent AEs will be reported in each treatment group by MedDRA System Organ Class and Preferred Term. Summaries will also be presented by the severity of the adverse event (per CTCAE, v4.03) and by relationship to study drug.

Laboratory shift tables containing counts and percentages will be prepared by treatment assignment, laboratory parameter, and time. Summary tables will be prepared for each laboratory parameter. Figures of changes in laboratory parameters over time will be generated.

Results of vital sign assessments and physical exams will be tabulated and summarized.

5.5.2 Demographics and Baseline Characteristics

Additional analyses will include summaries of subject demographics, baseline characteristics, compliance, and concurrent treatments. Concomitant medications will be coded according to the World Health Organization (WHO) Drug Dictionary and tabulated.

5.5.3 Analysis of Efficacy Parameters

5.5.3.1 Overall Response Rate

Tumor control will be documented at each assessment by response category (eg, CR, sCR, VGPR, PR, MR, SD, and disease progression) as defined for each response parameter, date that response is first documented, and date of MM disease progression.

The overall response rate (ORR) will be defined as the proportion of subjects who achieve a CR, sCR, VGPR, or PR. ORR will be calculated and the corresponding 95% two-sided confidence interval will be derived.

5.5.3.3 Clinical Benefit Rate

Clinical benefit rate (CBR) will be defined as the proportion of subjects who achieve a CR, sCR, VGPR, PR, or MR. CBR will be calculated and the corresponding 95% twosided confidence interval will be derived.

5.5.3.4 Disease Control Rate

Disease control rate (DCR) will be defined as the proportion of subjects who achieve a CR, sCR, VGPR, PR, MR, or SD. DCR will be calculated and the corresponding 95% two-sided confidence interval will be derived.

5.5.3.5 Progression-free Survival

Progression-free survival (PFS) is defined as the interval from the date of randomization to the earlier of the first documentation of objective MM disease progression or death from any cause. Kaplan-Meier methods will be used to estimate the event-free curves and corresponding quantiles (including the median). Data from surviving, nonprogressing subjects will be censored at the earliest of the time of initiation of anticancer treatment other than the study treatment or the last time that lack of MM progression was objectively documented. Data from subjects who have MM progression or die after \geq 2 consecutive missing tumor assessments will be censored at the last time prior to the missing assessments that lack of MM progression was objectively documented.

5.5.4 Analysis of Pharmacokinetic/Pharmacodynamic Parameters

The plasma PK of ACP-196 and dexamethasone will be characterized using noncompartmental analysis. The following PK parameters will be calculated, whenever possible, from plasma concentrations of ACP-196:

Product: ACP-196 (acalabrutinib) Date: 13 January 2016 Protocol: ACE-MY-001

- AUC_{0-t} Area under the plasma concentration-time curve calculated using linear trapezoidal summation from time 0 to time t, where t is the time of the last measurable concentration (C_t).
- AUC₀₋₁₂ Area under the plasma concentration-time curve from 0 to 12 hours, calculated using linear trapezoidal summation.
- AUC_{0- ∞} Area under the plasma concentration-time curve from 0 to infinity, calculated using the formula: AUC_{0- ∞} = AUC_{0-t} + C_t / λ_z , where λ_z is the apparent terminal elimination rate constant.
- $AUC_{0-24calc}$ Area under the plasma concentration-time curve from 0 to 24 hours, calculated by doubling the value for AUC_{0-12} .
- C_{max} Maximum observed plasma concentration
- T_{max} Time of the maximum plasma concentration (obtained without interpolation)
- t_{1/2} Terminal elimination half-life (whenever possible)
- λ_z Terminal elimination rate constant (whenever possible)
- CL/F Oral clearance

Missing dates or times may be imputed for PK and PD samples if the missing values can be established with an acceptable level of accuracy based on other information obtained during the visit in question. If PK and PD sampling for a given subject is not performed according to protocol instructions that subject may be excluded from the PK and PD analyses.

The PK parameters will be tabulated and summarized using descriptive statistics.

For each PD variable, the concentration at each assessment will be described. The change from baseline to each assessment will be summarized. The best change from baseline during the study will also be summarized. As appropriate, the on-treatment values will be compared with the pretreatment baseline values using paired t-tests.

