 Ongoing immunosuppressive therapy, including systemic or enteric corticosteroids for treatment of MM or other conditions. Note: Subjects may use topical or inhaled corticosteroids as therapy for comorbid conditions. During study participation, subjects may receive systemic or enteric corticosteroids as needed for MM therapy or treatment-emergent comorbid conditions. Grade ≥ 2 toxicity (other than alopecia) continuing from prior 		
anticancer therapy including radiation.		
 Known history of human immunodeficiency virus (HIV), serologic status reflecting active hepatitis B or C infection, or any uncontrolled active systemic infection. Subjects with hepatitis B core antibody positive who are surface antigen negative or who are hepatitis C antibody positive will need to have a negative polymerase chain reaction (PCR) result before enrollment. Those who are hepatitis B surface antigen positive or hepatitis B PCR positive and those who are hepatitis C PCR positive will be excluded. 		
 Major surgery within 4 weeks before first dose of ACP-196. 		
 Known history of a bleeding diathesis (eg, hemophilia, von Willebrand disease) 		
 History of stroke or intracranial hemorrhage within 6 months before the first dose of ACP-196. 		
 Requires or receiving anti-coagulation with warfarin or equivalent vitamin K antagonist (eg, phenprocoumon) within 28 days of first dose of study drug. 		
• Requires treatment with long-acting proton pump inhibitors (eg, omeprazole, esomeprazole, lansoprazole, dexlansoprazole, rabeprazole, or pantoprazole)		
 ANC < 0.75 x 10⁹/L or platelet count < 50 x 10⁹/L. For subjects with > 50% plasma cells in the marrow, ANC < 0.50 x 10⁹/L or platelet count < 30 x 10⁹/L. 		
 Creatinine > 2.5 x institutional upper limit of normal (ULN); total bilirubin > 2.5 x ULN; or aspartate aminotransferase (AST) or alanine aminotransferase (ALT) > 3.0 x ULN. 		
Breastfeeding or pregnant.		
Concurrent participation in another therapeutic clinical trial.		
ACP-196 is provided as 100-mg hard gelatin capsules prepared using standard pharmaceutical grade excipients.		
ACP-196 is an orally administered product. ACP-196 can be administered with or without food.		
Regimens:		
 Cohort 1 (BID): 100 mg ACP-196 (1 x 100-mg capsule) administered 12 hours apart (BID dosing = 200-mg total daily dose) 		

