4.1.19 Pharmacokinetics

Refer to the laboratory binder for instructions on collecting and processing these samples. Testing will be performed at the central clinical laboratory. Leftover plasma samples may be used for exploratory ACP-196 metabolite analyses. The PK sampling timepoints are provided in Table 4-1.

					HOURS P	OSTDOSE		
Cycle	Day	Predose	0.5 (±5 min)	0.75 (±5 min)	1 (±5 min)	2 (±10 min)	4 (±10 min)	6 (±10 min)
1	1	Х	Х	Х	Х	Х	Х	Х
	8	Х			Х			
	15	Х			Х			
	22	Х	Х	Х	Х	Х	Х	Х
	28	Х			Х			

Table 4-1.	Pharmacokinetic	Sample Schedule
------------	-----------------	-----------------

Note: These timepoints are relative to the morning dose.

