 - skin, eyes, ears, nose, throat, lungs, heart, abdomen, extremities, musculoskeletal system, lymphatic system, and nervous system. Symptom-directed physical exams The screening physical examination will include, at a minimum, the general appearance of the subject, height (screening only) and weight, and examination of the are done thereafter. ъ.
 - Vital signs (blood pressure, pulse, respiratory rate, and temperature) will be assessed after the subject has rested in the sitting position. Subjects should be in supine position and resting for ≥ 10 minutes before study-related ECGs.
 - Women of childbearing potential only. If positive, pregnancy must be ruled out by ultrasound to be eligible. نے بن ہے
- Hematology includes complete blood count with differential and platelet and reticulocyte counts. Cycle 1 Day 1 hematology does not need to be repeated if screening hematology was within 5 days.
 - blood urea nitrogen (BUN), calcium, chloride, creatinine, C-terminal telopeptide, glucose, lactate dehydrogenase (LDH), magnesium, phosphate, potassium, sodium, Serum chemistry: albumin, alkaline phosphatase, bone-specific alkaline phosphatase, alanine transaminase (ALT), aspartate aminotransferase (AST), bicarbonate, total bilitubin, total protein, and uric acid. Cycle 1 Day 1 serum chemistry does not need to be repeated if screening serum chemistry was within 5 days. Urinalysis: pH, ketones, specific gravity, bilirubin, protein, blood, N-terminal telopeptide, and glucose. .____
 - I/B/NK cell count (ie, CD3, CD4, CD8, CD19, CD16/56). During Cycle 5-12, only done at end of Cycle 6 and 12.
 - Refer to Section 4.1 for a list of myeloma disease markers.
 - Pharmacodynamic samples are drawn predose and 4 hours (±10 minutes) postdose on the days indicated. Note: These timepoints are relative to the morning dose. Ŀ.
 - Pharmacodynamic samples are drawn predose on the days indicated. Pharmacokinetic samples are drawn per Table 4-1.
- Refer to Section 4-2. Bone marrow aspirate/biopsy and skeletal survey are required at baseline (ie, before the first dose of study drug). Thereafter they are required as indicated in the table above. о d
 - The indicated samples at this timepoint (Cycle 1 Day 1) must be drawn predose.

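### AUC0-12, and AUC0-24calc as twice that value, cannot be obtained by the stated linear trapezoidal rule because PK sampling stops at 6 hours

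*Protocol*

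**What the plan says.** Protocol Section 5.5.4 introduces its list with "The following PK parameters will be calculated, whenever possible, from plasma concentrations of ACP-196". The list includes AUC0-12, defined as "Area under the plasma concentration-time curve from 0 to 12 hours, calculated using linear trapezoidal summation", and AUC0-24calc, the area under the "curve from 0 to 24 hours, calculated by doubling the value for" AUC0-12. The synopsis gives the same two definitions. The terminal rate constant λz enters an area formula only once, for AUC0-∞.

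Section 4.1.19 says "The PK sampling timepoints are provided in Table 4-1". On Cycle 1 Days 1 and 22 that table has predose, 0.5, 0.75, 1, 2, 4 and 6 h. On Days 8, 15 and 28 it has predose and 1 h only. Its footnote reads "Note: These timepoints are relative to the morning dose". Appendix 5 adds no later time: "Pharmacokinetic samples are drawn per Table 4-1". In the synopsis regimens, ACP-196 doses are "administered 12 hours apart".

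The SAP (Sections 1 and 4.3) refers PK to separate reports and gives no rule for these parameters.

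**The concern.** A trapezoid cannot run past its last observed point. With a 12-hour dosing interval and a last sample at 6 h, half of every interval is unobserved, and the named method stops at 6 h. The analyst must then leave AUC0-12 blank, report a 0-6 hour area under the wrong label, or supply a rule that the plan does not contain. These choices give different numbers, and doubling carries the same relative difference into AUC0-24calc.

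Characterising ACP-196 PK with and without dexamethasone is a secondary objective (Section 2.2). Section 3.3 adds that the randomised design will let the interaction potential be assessed. An exposure parameter with an undefined derivation weakens both, and makes comparison with other ACP-196 studies uncertain.

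**Working it through.** The plan states no numerical result here to reproduce. The check has two parts.

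**1. Sampling grid against integration limit.** Required upper limit: 12 h (Section 5.5.4). Last scheduled sample: 6 h (Table 4-1). Unobserved: 12 − 6 = 6 h, half the interval. The table's columns are the same in all three protocol versions supplied, so this is not a text-extraction fault.

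**2. Size of the missing area.** Inputs:
- Half-life: 0.97 to 2.1 h in Part 1 of the healthy-volunteer study (2.5 to 50 mg as 2 daily doses, plus a single 100 mg dose), and 3.3 and 2.5 h in Part 3 at 50 mg, without and with itraconazole (Section 1.3.1).
- Tmax: assumed 0.75 h, the middle of the 0.5 to 1.0 h reported for Part 1.
- Dosing interval: 12 h.

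One-compartment oral model at steady state, in units of (bioavailable dose)/volume:

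- ke = ln 2 / t½, and ka solves ln(ka/ke)/(ka − ke) = 0.75.
- C(t) = [ka/(ka − ke)] × [e^(−ke·t)/(1 − e^(−12ke)) − e^(−ka·t)/(1 − e^(−12ka))].
- AUC0-12 = 1/ke, and the share after 6 h = 1 − AUC0-6/AUC0-12.
- λz tail = (C6/λz)(1 − e^(−6λz)), added to the trapezoid on the Table 4-1 grid.
- Predose substitution: add 6 × (C6 + C0)/2, with the Day 22 predose value C0 as the 12-hour concentration.

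| t½ (h) | ke | ka | AUC0-12 | AUC0-6 | Share after 6 h | Trapezoid 0-6 h ÷ AUC0-12 | With λz tail | With predose as C12 |
|---|---|---|---|---|---|---|---|---|
| 0.97 | 0.715 | 2.235 | 1.399 | 1.372 | 2.0% | 99.7% | 101.7% | 104.1% |
| 1.5 | 0.462 | 2.920 | 2.164 | 2.013 | 7.0% | 93.1% | 100.1% | 104.1% |
| 2.1 | 0.330 | 3.465 | 3.030 | 2.624 | 13.4% | 85.9% | 99.3% | 103.5% |
| 2.5 | 0.277 | 3.750 | 3.607 | 2.986 | 17.2% | 81.9% | 99.1% | 102.9% |
| 3.3 | 0.210 | 4.206 | 4.761 | 3.654 | 23.3% | 75.7% | 99.0% | 102.0% |

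Worked row, t½ = 2.1 h:
- Share after 6 h: 1 − 2.624/3.030 = 13.4%.
- λz tail: (0.1555/0.3301) × 0.8620 = 0.406. The trapezoid to 6 h is 2.603, so (2.603 + 0.406)/3.030 = 99.3%.
- Predose route: 2.603 + 6 × (0.1555 + 0.0215)/2 = 3.134, and 3.134/3.030 = 103.5%.

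At 0.97 h the linear rule's overshoot on this grid offsets most of the missing 2%. Fixing ka at 3/h instead of Tmax gives shares of 1.8% to 23.8%, so the absorption assumption matters little. Half-life drives the result.

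**3. When a cohort comparison would be distorted.** If half-life is the same in both cohorts, the omitted share is the same and cancels in a ratio. Purely as an illustration, suppose half-life fell from 2.5 to 1.5 h with dexamethasone. The true ratio is 1.5/2.5 = 0.60. The 0-6 hour trapezoid would show 0.60 × 93.1/81.9 = 0.68, and with the λz tail 0.60 × 100.1/99.1 = 0.61.

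**The case against.** The strongest reply has four parts.

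- **AUC0-12 is recoverable.** On Day 22 the predose sample is a 12-hour trough from the previous evening's dose. Used as the 12-hour value at steady state, it lets the linear trapezoid run the full interval and recovers 102% to 104%. This stands. A reader might infer that the plan can yield only no AUC0-12 or a mislabelled AUC0-6, and that goes too far. But the substitution is not written down, and the caveat about calculating parameters when possible covers missing data, not a method that fails for every compliant subject.
- **The bias mechanism lacks support.** A reader might infer that dexamethasone, by inducing CYP3A4, would shorten half-life and bias the comparison. Section 1.3.1 reports that itraconazole cut CL/F from 217 to 44 L/h, with no half-life difference noted (3.3 against 2.5 h). Section 3.3 calls dexamethasone a weak inducer. Section 5.5.4 plans descriptive PK summaries only, and Section 5.2 says the study is not formally designed to compare regimens. This stands: the distortion is conditional, and no exposure ratio is specified.
- **The upper figure is unlikely at 100 mg.** The 3.3 h half-life comes from 50 mg, and Section 1.3.1 says half-life appeared to fall with dose. In Table 1-4, 100 mg BID with sampling also to 6 h gives mean AUC/mean Cmax = 837/716 = 1.17 h. The model gives 2.34 h even at t½ 0.97 h, so patient profiles may be narrower than any modelled. This also stands, as a crude ratio of means.
- **The rule may exist elsewhere.** The Amendment 1 summary foresees a separate analysis plan for PK/PD, and the SAP points to separate reports. Neither was supplied, so this cannot be excluded. The protocol would still name a method that its schedule cannot support.

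**Conclusion.** The point holds as an inconsistency within the protocol: neither AUC0-12 nor AUC0-24calc can be obtained by the method stated in Section 5.5.4 from the samples in Table 4-1. Section 1.3.2 describes a comparable situation more accurately: under Table 1-4, also sampled to 6 h, it relates 24-hour BID exposure to twice AUC0-6.

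If the 0-6 hour area were relabelled and doubled, the omitted share would be about 2% to 13% over the Part 1 half-lives, and up to 23% at the 50 mg value of 3.3 h. At 100 mg the lower end is more plausible. The figures rest on a one-compartment shape and an assumed Tmax of 0.75 h. Section 1.3.1 reports a median Tmax of 2.5 h in the fed state, and dosing with food is allowed, so later-peaking profiles would leave more area after 6 h.

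The documents do not show a half-life difference between cohorts, so a biased dexamethasone comparison is not established. This is a worthwhile correction to a descriptive secondary parameter and leaves the primary safety objective untouched.

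**What to change.** Amend the PK analysis wording in Section 5.5.4 and the synopsis, or place the rule in the PK analysis plan and refer to it:

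1. Report the observed area under its own name (AUC0-t, here AUC0-6). AUC0-t is already on the list.
2. Define AUC0-12 = AUC0-6 + (C6/λz)(1 − e^(−6λz)) where λz is estimable, and report the extrapolated percentage for each subject. Alternatively, on Day 22, use the steady-state predose concentration as the 12-hour value and say so. Choose one as the main rule. The predose route is not available on Day 1, when that sample precedes any drug.
3. Derive AUC0-24calc only from the Day 22 AUC0-12, since doubling presumes that the two dosing intervals are alike.
4. When describing the cohorts, show AUC0-12 or AUC0-∞ beside AUC0-6. Relying on AUC0-6 alone would keep the truncation.

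The cost is wording and programming. No new samples are needed, so the change remains feasible although enrolment has stopped (SAP Section 3.1).
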